
**Table 13: Assessment of Severity and Causality of AEs and/or SAEs/AESIs**

Severity	
All AEs, including clinically significant treatment-emergent laboratory abnormalities, will be graded according to the NCI-CTCAE, version 5.0 ( https://ctep.cancer.gov/protocoldevelopment/electronic_applications/docs/CTCAE_v5_Quick_Reference_5x7.pdf )	
Adverse events not listed by the NCI-CTCAE will be graded according to the criteria defined below.	
Grade	Description
1	Mild; asymptomatic or mild symptoms; clinical or diagnostic observations only; intervention not indicated.
2	Moderate; minimal, local or noninvasive intervention indicated; limiting age appropriate instrumental activities of daily living.
3	Severe or medically significant but not immediately life-threatening; hospitalization or prolongation of hospitalization indicated; disabling; limiting self-care activities of daily living.
4	Life-threatening consequences; urgent intervention indicated.
5	Fatal AE; an event that results in the death of the participant.
Note: Instrumental activities of daily living refer to preparing meals, shopping for groceries or clothes, using the telephone, managing money, etc. Self-care activities of daily living refer to bathing, dressing and undressing, feeding self, using the toilet, taking medications, and not bedridden.	
Causality	

 
The investigator is obligated to assess the relationship between trial intervention and each occurrence of each AE/SAE/AESI.
 
The investigator will assess the relationship as either of the following: 
 
Related: An AE will be considered “related” to the use of the IMP if there is evidence to suggest a reasonable possibility of a causal relationship between the IMP and the AE.
 
Not Related: An AE will be considered “not related” to the use of the IMP if there is no plausible causal relationship between the IMP and the AE.
 
 
 
The investigator will use clinical judgment to determine the relationship.
 
Alternative causes, such as underlying disease(s), concomitant therapy, and other risk factors, as well as the temporal relationship of the event to trial intervention administration will be considered and investigated.
 
The investigator will also consult the IB and/or Product Information, for marketed products, in his/her assessment.
 
For each AE/SAE/AESI, the investigator must document in the medical notes that he/she has reviewed the AE/SAE/AESI and has provided an assessment of causality.
 
There may be situations in which an SAE/AESI has occurred and the investigator has minimal information to include in the initial report to the sponsor or designee. However, it is very important that the investigator always make an assessment of causality for every event before the initial transmission of the SAE/AESI data to the sponsor or designee.
 
	

### Causality

- The investigator may change his/her opinion of causality in light of follow-up information and send an SAE/AESI follow-up report with the updated causality assessment.
- The causality assessment is one of the criteria used when determining regulatory reporting requirements

**Table 14: Follow-Up of AEs and SAEs/AESIs**

### Follow-Up

- The investigator is obligated to perform or arrange for the conduct of supplemental measurements and/or evaluations as medically indicated or as requested by the sponsor or designee to elucidate the nature and/or causality of the AE or SAE/AESI as fully as possible. This may include additional laboratory tests or investigations, histopathological examinations, or consultation with other health care professionals.
- If a participant dies during participation in the trial or during a recognized follow-up period, the investigator will provide the sponsor or designee with a copy of any postmortem findings including histopathology.
- New or updated information will be recorded in the originally completed eCRF.
- The investigator will submit any updated SAE/AESI data to the sponsor or designee within 24 hours of receipt of the information.

### 10.3.4. Reporting of SAEs/AESIs

**Table 15: SAE/AESI Reporting to the Sponsor or Designee via an Electronic Data Collection Tool**

### Reporting to the Sponsor or Designee via an Electronic Data Collection Tool

- The primary mechanism for reporting an SAE/AESI to the sponsor or designee will be the electronic data collection tool.
- The site will enter the SAE/AESI data as soon as it becomes available within 24 hours of awareness.
- If the electronic data collection tool is unavailable, then the site will use the paper form (see [Table 16](#)).
- After the trial is completed at a given site, the electronic data collection tool will be taken offline to prevent the entry of new data or changes to existing data.
- If a site receives a report of a new SAE/AESI from a trial participant or receives updated data on a previously reported SAE/AESI after the electronic data collection tool has been taken offline, then the site can report this information on the paper form (see [Table 16](#)) or to the sponsor or designee by telephone.

**Table 16: SAE/AESI Reporting to the Sponsor or Designee via Paper Form (if needed)**

Reporting to the Sponsor or Designee via Paper Form

• If the electronic data collection tool is unavailable, then the site will use the paper form. The paper form should be used to electronically transmit this information to the sponsor or designee.

• Contacts for electronic transmission of the paper form are provided in the Operations Manual.

• In rare circumstances and in the absence of facsimile equipment, notification by telephone is acceptable with a copy of the data collection tool sent by overnight mail or courier service.

• Initial notification via telephone does not replace the need for the investigator to complete and sign the appropriate form within the designated reporting time frames.

## **10.4. Contraceptive Guidance and Collection of Pregnancy Information**

### **10.4.1. Definitions**

#### **10.4.1.1. Women of Childbearing Potential, Women of Nonchildbearing Potential, and Fertile Men**

A woman is considered to be a woman of childbearing potential following menarche and until becoming postmenopausal unless permanently sterile.

A woman is considered to be of nonchildbearing potential if she fulfills either of the following criteria:

- Underwent permanent sterilization including hysterectomy, bilateral oophorectomy, or bilateral salpingectomy.
- Is in a postmenopausal state, which is defined as no menses for at least 12 consecutive months without an alternative medical cause, and confirmed with an FSH level >40 mIU/mL.

A man is considered fertile after puberty unless permanently sterile by bilateral orchidectomy.

#### **10.4.1.2. Highly Effective Form of Contraception (Failure Rate <1%)**

A highly effective form of contraception (failure rate of <1%) is defined as follows:

- Combined (estrogen and progestogen containing) hormonal contraception associated with inhibition of ovulation:
  - Oral
  - Intravaginal
  - Transdermal
- Progestogen-only hormonal contraception associated with inhibition of ovulation:
  - Oral
  - Injectable
  - Implantable
- Intrauterine device
- Intrauterine hormone-releasing system
- Bilateral tubal occlusion (eg, bilateral tubal ligation, clips)
- Vasectomized partner
- Sexual abstinence is considered a highly effective method only if defined as refraining from heterosexual intercourse during the entire period of risk associated with the trial intervention. The reliability of sexual abstinence needs to be evaluated

in relation to the duration of the clinical trial and the preferred and usual lifestyle of the participant.

#### **10.4.2. Collection of Pregnancy Information**

##### **10.4.2.1. Male Participants With Partners Who Become Pregnant**

- The investigator will attempt to collect pregnancy information on any male participant's female partner who becomes pregnant while the male participant is in this trial. This applies only to male participants who receive trial intervention.
- After obtaining the necessary signed informed consent from the pregnant female partner directly, the investigator will record pregnancy information on the appropriate form and submit it to the sponsor within 24 hours of learning of the partner's pregnancy. The female partner will also be followed to determine the outcome of the pregnancy. Information on the status of the mother and child will be forwarded to the sponsor. Generally, the follow-up will be no longer than 6 to 8 weeks following the estimated delivery date. Any termination of the pregnancy will be reported regardless of fetal status (presence or absence of anomalies) or indication for the procedure.

##### **10.4.2.2. Female Participants Who Become Pregnant**

- The investigator will collect pregnancy information on any female participant who becomes pregnant while participating in this trial. Information will be recorded on the appropriate form and submitted to the sponsor within 24 hours of learning of a participant's pregnancy.
- The participant will be followed to determine the outcome of the pregnancy. The investigator will collect follow-up information on the participant and the neonate and the information will be forwarded to the sponsor. Generally, follow-up will not be required for longer than 6 to 8 weeks beyond the estimated delivery date. Any termination of pregnancy will be reported, regardless of fetal status (presence or absence of anomalies) or indication for the procedure.
- While pregnancy itself is not considered to be an AE or SAE, any pregnancy complication or elective termination of a pregnancy will be reported as an AE or SAE. A spontaneous abortion is always considered to be an SAE and will be reported as such. Any post-trial pregnancy-related SAE considered reasonably related to the trial intervention by the investigator will be reported to the sponsor as described in [Section 8.3.4](#). While the investigator is not obligated to actively seek this information in former trial participants, he or she may learn of an SAE through spontaneous reporting.
- Any female participant who becomes pregnant while participating in the trial will discontinue trial intervention and be withdrawn from the trial.

## **10.5. Future Biospecimen Research**

### **Use/Analysis of DNA**

- Genetic variation may impact a participant's response to IMP, susceptibility to, and severity and progression of disease. Variable response to IMP may be due to genetic determinants that impact drug absorption, distribution, metabolism, and excretion; mechanism of action of the intervention; disease etiology; and/or molecular subtype of the disease being treated. Therefore, where local regulations and IRB/IEC allow, a sample will be collected for DNA analysis from consenting participants.
- DNA samples will be used for research related to darigabat or panic disorder and related diseases. They may also be used to develop tests/assays including diagnostic tests related to darigabat and/or interventions of this drug class and panic disorder. Genetic research may consist of the analysis of one or more candidate genes or the analysis of genetic markers throughout the genome or analysis of the entire genome (as appropriate).
- The samples may be analyzed as part of a multitrial assessment of genetic factors involved in the response to darigabat or interventions of this class to understand trial disease or related conditions.
- The results of genetic analyses may be reported in the CSR or in a separate trial summary.
- The sponsor will store the DNA samples in a secure storage space with adequate measures to protect confidentiality.
- The samples will be retained while research on darigabat or interventions of this class or indication continues but no longer than 15 years or other period as per local requirements.

## 10.6. Liver Safety: Suggested Actions and Follow-up Assessments

### 10.6.1. Assessment of Elevations in Liver Test Results

Elevations in liver test results occurring during a clinical trial may result from DILI. However, since DILI is a diagnosis of exclusion, it is essential to exclude other etiologies (see [Section 10.6.4](#)) that may lead to elevated results in liver tests.

When aminotransferase (ALT or AST) levels increase to  $\geq 3 \times \text{ULN}$  during a clinical trial, current US guidance ([US FDA, 2009](#)) recommends close observation and diagnostic workup for causes of hepatic injury (see [Section 10.6.4](#)) other than the IMP. The International Consensus Criteria for idiosyncratic DILI only uses ALT to define DILI when referring to aminotransferase levels ([Watkins, 2019](#)). The CIOMS Working Group on DILI suggests using serum ALT as it is more specific than AST to detect and monitor the liver injury, irrespective of the cause ([CIOMS, 2020](#); [EASL, 2019](#); [Kwo et al, 2017](#)).

The medical monitor must be consulted when ALT levels increase to  $\geq 3 \times \text{ULN}$ .

[Table 17](#) describes liver test monitoring during the close observation period of elevated liver tests during a clinical trial. Close observation is required until the elevations in liver test results return to baseline levels or normalize.

**Table 17: Monitoring of Liver Tests**

Result	Frequency for Repeating Liver (AST, ALT, Bilirubin [Total and Direct]) and INR Tests
If either of the following: 
 
ALT <math>\geq 3 \times \text{ULN}</math> and total bilirubin <math>\geq 2 \times \text{ULN}</math> or INR <math>> 1.5</math>
 
ALT <math>\geq 3 \times \text{ULN}</math> with symptoms and signs of hepatitis
 
	Every 24 hours until laboratory abnormalities improve
If ALT $\geq 3 \times \text{ULN}$ and total bilirubin or INR are within the normal range	Every 48 to 72 hours until laboratory abnormalities improve
If the liver test abnormalities improve AND participants' symptoms improve or participants are asymptomatic	Frequency may decrease to once weekly

Abbreviations: ALT=alanine aminotransferase; AST=aspartate aminotransferase; INR=international normalized ratio; ULN=upper limit of normal.

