### 8.3.7. Adverse Events of Special Interest

All AESIs should be reported according to the procedures and timelines for SAEs (see [Section 10.3.4](#)).

The following events will be reported as AESIs:

- AEs that result in the discontinuation of IMP
- AEs potentially related to abuse (refer to the Abuse Potential Monitoring Plan [APMP] document for details)
- AEs of suicidality
- C-SSRS (Since Last Visit) "Yes" answer to Suicidal Ideation Items #4 or #5 or any Suicidal Behaviors
- QTcF >500 ms or an increase >60 ms from Baseline
- Liver enzymes:
  - ALT or AST  $\geq 3 \times$  ULN and serum bilirubin  $\geq 2 \times$  ULN (suspected Hy's Law)
  - ALT  $\geq 5 \times$  ULN
- Hematologic abnormalities:
  - Absolute neutrophil count  $< 1.5 \times 10^9/L$
  - Platelet count  $< 100 \times 10^9/L$
  - Hemoglobin  $< 10$  g/dL

For QTcF, liver enzymes, and/or hematological abnormalities meeting the above AESI criteria, a repeat evaluation should be immediately performed for confirmation and the medical monitor notified. See [Section 10.6.1](#) for further details on the assessment of elevations in liver test results.

If the repeat evaluation is confirmed abnormal, the treatment with study drug should be discontinued and the early termination visit should be completed.

An APMP will be used to monitor events that may suggest that darigabat produces drug effects that could be sought out for abuse purposes. As part of the APMP, AEs potentially related to abuse and medication handling irregularities related to suspected or known abuse of IMP must be reported as AESIs. Investigators and site staff at each trial site will be trained on reporting potentially abuse-related AEs. While the investigators will be provided with examples of AE

terms as a guide during trial conduct, the analysis of potentially abuse-related AEs will be based on a search by the sponsor of all relevant MedDRA terms, all verbatim terms, and any open text fields within the AE data to identify text strings suggestive of abuse potential, consistent with US FDA guidance ([US FDA Guidance for Industry, 2017](#)).

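### Protocol Table 17 gives two different liver retest intervals for some results with ALT ≥3×ULN, including potential Hy's law results, and leaves one ALT-led combination and AST-led cases without an interval

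*Protocol*

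**What the plan says.** Table 17 in Protocol Section 10.6.1 has three rows.

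- Row 1 opens with "If either of the following" and lists two conditions: ALT ≥3×ULN with total bilirubin ≥2×ULN or INR >1.5, and ALT ≥3×ULN with "symptoms and signs of hepatitis". The instruction is "Every 24 hours until laboratory abnormalities improve".
- Row 2 applies if ALT is ≥3×ULN and "total bilirubin or INR are within the normal range". The instruction is "Every 48 to 72 hours until laboratory abnormalities improve".
- Row 3 applies once the abnormalities have improved: "Frequency may decrease to once weekly".

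Three other sections bear on the table. Section 10.6.2 lists the potential Hy's law criteria: ALT ≥3×ULN, bilirubin ≥2×ULN or INR >1.5, alkaline phosphatase <2×ULN, and no alternative cause. Section 8.3.7 makes ALT or AST ≥3×ULN with bilirubin ≥2×ULN an adverse event of special interest (AESI), labelled "suspected Hy's Law". The text of Section 10.6.1 reports US guidance that begins "When aminotransferase (ALT or AST) levels increase to" 3×ULN, then cites consensus sources that prefer ALT, and sets its own medical monitor rule on ALT.

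**The concern.** Table 17 is the only place in the protocol that sets a serial retest interval after a transaminase rise. If one result fits two rows, two sites can both comply and yet retest at 24 hours and at 72 hours. The intervals differ by a factor of 2 to 3 (48/24 and 72/24). The conflict reaches results that meet the enzyme and bilirubin/INR criteria of Section 10.6.2, which are the results this part of the protocol is meant to catch. A result that fits no row leaves the site without a stated interval at all.

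**Working it through.** There is no sample size or power figure to reproduce. The check is to list every combination and see which rows it meets.

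**Inputs.** All cases have ALT ≥3×ULN. Bilirubin has three levels: normal, above ULN but below 2×ULN (mid), and ≥2×ULN. INR has three: normal, above normal up to 1.5 (mid), and >1.5. Hepatitis symptoms are absent or present. That gives 3 × 3 × 2 = 18 combinations. The cut-offs come from Table 17. The mid INR band is not empty if the laboratory's upper limit is below 1.5; SAP Section 9.5 grades INR >1.2 to 1.5 as increased.

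**Rules.** Row 1 is met if bilirubin is ≥2×ULN, or INR is >1.5, or symptoms are present. This groups the bilirubin and INR conditions as the brackets in Table 18 do. Row 2 as written is met if bilirubin is normal or INR is normal. Row 3 needs prior improvement, so it cannot fill a gap at first elevation.

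**No symptoms, row 2 as written:**

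| Bilirubin | INR normal | INR mid | INR >1.5 |
|---|---|---|---|
| Normal | row 2 | row 2 | **both** |
| Mid | row 2 | **neither** | row 1 |
| ≥2×ULN | **both** | row 1 | row 1 |

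So 2 of 9 meet both rows, 3 meet row 1 only, 3 meet row 2 only, and 1 meets neither.

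**With symptoms, row 2 as written.** Row 1 is always met. Row 2 is also met in the 5 cells where bilirubin or INR is normal, so 5 meet both and 4 meet row 1 only.

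**Total, row 2 as written.** Both rows 2 + 5 = 7; row 1 only 3 + 4 = 7; row 2 only 3; neither 1; sum 18.

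**Potential Hy's law cells.** Bilirubin ≥2×ULN or INR >1.5 covers 5 of 9 cells, so 10 of 18 with symptoms counted. Of these, 4 meet both rows (bilirubin ≥2×ULN with normal INR, and INR >1.5 with normal bilirubin, each with and without symptoms), 6 meet row 1 only, and none is without a row. The one uncovered cell (mid bilirubin, mid INR, no symptoms) does not meet Section 10.6.2.

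**Row 2 read as both values normal:**

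| | As written | Both normal |
|---|---|---|
| Both rows | 7 | 1 |
| Row 1 only | 7 | 13 |
| Row 2 only | 3 | 1 |
| Neither | 1 | 3 |
| Potential Hy's law cells in both rows | 4 of 10 | 0 of 10 |

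The remaining overlap is a symptomatic participant with both values normal. The three uncovered cells, all without symptoms, are normal bilirubin with mid INR, mid bilirubin with normal INR, and mid with mid.

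**AST.** Take AST ≥3×ULN, bilirubin ≥2×ULN and ALT <3×ULN. Section 8.3.7 makes this an AESI with an immediate confirmatory repeat. Rows 1 and 2 both require ALT ≥3×ULN, so no serial interval applies.

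**The case against.** The natural reading of row 2 is that neither value is abnormal: the verb is plural and the rows run from more to less severe. On that reading every potential Hy's law combination is 24 hours only. This is a fair account of what was probably meant, and it removes the most serious overlap. It does not repair the table, because three combinations then have no row and one symptomatic overlap stays.

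The protocol also has safeguards. The medical monitor must be consulted whenever ALT reaches 3×ULN (Section 10.6.1). AESI results need an immediate repeat, medical monitor notification, and discontinuation if confirmed (Sections 7.1 and 8.3.7). Table 18 withholds drug in the potential Hy's law states and in symptomatic acute hepatitis. Section 8.2.5 requires clinically significant abnormal results to be repeated until they resolve. Section 10.6 is itself headed as suggested actions. These points stand and reduce the chance that sites diverge unnoticed. None of them gives a serial interval.

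A reader might go further in three ways that the documents do not support:

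- That an ALT-led potential Hy's law case can be left with no interval. Any result with ALT ≥3×ULN that meets the bilirubin/INR criterion of Section 10.6.2 meets row 1 under either reading.
- That participants with bilirubin just below 2×ULN generally have no interval. As written, they fall in row 2 if INR is normal and in row 1 if INR is >1.5 or symptoms are present. Only the asymptomatic subset with INR above normal but not above 1.5 is uncovered.
- That Section 10.6.1 itself sets an ALT-or-AST trigger. It reports this as outside guidance and then explains why ALT is preferred, so keying the table on ALT is a stated choice. What is left is the mismatch with Section 8.3.7.

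**Conclusion.** The point holds as a contradiction in a safety instruction. As written, 7 of 18 combinations carry two intervals, 4 of them in potential Hy's law territory, and 1 carries none. An AST-led AESI has an immediate repeat but no serial interval.

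These are counts of combinations, not of participants. The documents give no event rate, so the number of people affected cannot be estimated. The single gap in the as-written reading assumes the laboratory's INR upper limit is below 1.5. If it were 1.5 that gap would close, but the overlap would remain. No endpoint, estimand or efficacy analysis is affected. The SAP records a February 2025 decision to close the study, not linked to safety, which lowers the urgency but does not remove the contradiction from the current protocol version.

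**What to change.** Reword Table 17 so that its rows are mutually exclusive and together cover every result with ALT ≥3×ULN. The wording should state how it treats one normal and one raised value, bilirubin between ULN and 2×ULN, INR between normal and 1.5, and symptomatic participants with a normal bilirubin or INR. Alternatively, add an explicit precedence rule and a row for the uncovered combinations.

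Reconcile Sections 8.3.7, 10.6.1 and 10.6.2 with Table 17 on AST-led elevations, either by giving them a row or by stating how they are followed after the confirmatory repeat. Which interval belongs to each combination is a clinical decision for the sponsor.

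The cost is the wording of one table and its cross-references, by amendment or clarification letter. No new procedure, visit or analysis is needed.
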